### 2.1 Primary Objective(s)

2.1.1 Measure the overall response rate for immunotherapy given with quad-shot radiotherapy

### 2.2 Secondary Objective(s)

2.2.1 Measure the response rate at the target lesion.

Quad-Shot Radiotherapy in Combination with Immune Checkpoint Inhibition for  
Advanced/Recurrent Head and Neck Cancer  
Wake Forest Baptist Comprehensive Cancer Center  
WFBCCC60320

- 2.2.2 Measure the response rate at non-target sites *in patients with non-target sites.*
- 2.2.3 Evaluate the durability of response at the target lesion.
- 2.2.4 Evaluate progression-free survival.
- 2.2.5 Evaluate overall survival.
- 2.2.6 Assess the tolerability of the combination of quad-shot radiotherapy with immunotherapy in order to assess the feasibility of this treatment regimen.

### **2.3 Exploratory Objectives**

- 2.3.1 Evaluate the effect of quad- shot administration on increasing the immune activation by treatment with pembrolizumab and investigate possible mechanisms.

## **3.0 Patient Selection**

In this pilot study of quad-shot radiotherapy in combination with pembrolizumab immunotherapy, patients with advanced, recurrent or metastatic head and neck cancer will be enrolled. Participants will be identified and selected for eligibility screening during routine clinical practice in either the medical oncology or radiation oncology clinics at WFBCCC.

### **3.1 Inclusion Criteria**

- 3.1.1 Advanced, recurrent or metastatic head and neck squamous cell carcinoma, as defined by clinical or pathological diagnosis of any of the following:
  - 3.1.1.1 Locally advanced head and neck squamous cell carcinoma not suitable for curative local treatment.
  - 3.1.1.2 Locally recurrent head and neck squamous cell carcinoma not suitable for curative local treatment within or outside a previously irradiated tissue.
  - 3.1.1.3 Metastatic head and neck squamous cell carcinoma.

Quad-Shot Radiotherapy in Combination with Immune Checkpoint Inhibition for  
Advanced/Recurrent Head and Neck Cancer  
Wake Forest Baptist Comprehensive Cancer Center  
WFBCCC60320

- 3.1.2 Target site in the head and neck region amenable to quad-shot palliative radiotherapy, for which palliative radiotherapy is recommended, as determined by the treating radiation oncologist.
- 3.1.3 Age 18 years or greater at time of registration
- 3.1.4 ECOG Performance Status of 0-2.
- 3.1.5 Women of child-bearing potential and men must agree to use adequate contraception (hormonal or barrier method of birth control; abstinence) prior to study entry and for the duration of study participation. Should a woman become pregnant or suspect she is pregnant while participating in this study, she should inform her treating physician immediately.
- 3.1.6 Ability to understand and the willingness to sign an IRB-approved informed consent document (either directly or via a legally authorized representative).
- 3.1.7 Willingness to provide blood and saliva samples for exploratory research purposes
- 3.1.8 Organ and Marrow Function as defined below:
  - 3.1.8.1 Absolute neutrophil count (ANC)  $\geq 1.5 \times 10^9/L$
  - 3.1.8.2 Platelet count  $\geq 100 \times 10^9/L$
  - 3.1.8.3 Hemoglobin  $\geq 9.0 \text{ g/dL}$
  - 3.1.8.4 Serum bilirubin  $\leq 1.5 \times \text{ULN}$  (institutional upper limit of normal)
  - 3.1.8.5 AST and ALT  $\leq 2.5 \times \text{ULN}$  (institutional upper limit of normal)
  - 3.1.8.6 Serum creatinine CL  $> 40 \text{ mL/min}$  by the Cockcroft-Gault formula (Cockcroft and Gault 1976) or by 24-hour urine collection for determination of creatinine clearance:

Males:

$$\text{Creatinine CL (mL/min)} = \frac{\text{Weight (kg)} \times (140 - \text{Age})}{72 \times \text{serum creatinine (mg/dL)}}.$$

Females:

$$\text{Creatinine CL (mL/min)} = \frac{\text{Weight (kg)} \times (140 - \text{Age})}{72 \times \text{serum creatinine (mg/dL)}} \times 0.85$$

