#### **4.4.7 Restrictions during the study**

##### **4.4.7.1 Contraception**

Females of childbearing potential who are sexually active with a nonsterilised male partner must use 2 methods of effective contraception from screening, and must agree to continue using such precautions for 180 days after the final dose of investigational product. Periodic abstinence, the rhythm method, and the withdrawal method are not acceptable methods of birth control.

- Females of childbearing potential are defined as those who are not surgically sterile (i.e., bilateral tubal ligation, bilateral oophorectomy, or complete hysterectomy) or postmenopausal (defined as 12 months with no menses without an alternative medical cause).
- Subjects must use 2 acceptable methods of effective contraception as described in the table below.
- Nonsterilised males who are sexually active with a female partner of childbearing potential must use 2 acceptable methods of effective contraception (see Table 1) from Day 1 and for 90 days after receipt of the final dose of investigational product.

Quad-Shot Radiotherapy in Combination with Immune Checkpoint Inhibition for  
Advanced/Recurrent Head and Neck Cancer  
Wake Forest Baptist Comprehensive Cancer Center  
WFBCCC60320

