#### **Embryo-fetal toxicity**

Pembrolizumab can cause fetal harm when administered to a pregnant woman due to an increased risk of immune-mediated rejection of the developing fetus resulting in fetal death. Advise women of the potential risk to a fetus. Advise females of reproductive potential to use effective contraception during treatment with pembrolizumab and for at least 4 months after the last dose.

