## Appendix A – Eligibility Checklist

IRB Protocol No.	WFBCCC Protocol No.
Study Title: Quad-Shot Radiotherapy in Combination with Immune Checkpoint Inhibition for Advanced/Recurrent Head and Neck Cancer	
Principal Investigator: [name]	

Inclusion Criteria (as outlined in study protocol)	Criteria is met	Criteria is NOT met	Source Used to Confirm * (Please document dates and lab results)
Advanced, recurrent or metastatic head and neck squamous cell carcinoma, as defined by clinical or pathological diagnosis of any of the following:			
Locally advanced head and neck squamous cell carcinoma not suitable for curative local treatment.			
Locally recurrent head and neck squamous cell carcinoma not suitable for curative local treatment within or outside a previously irradiated tissue.			
Metastatic head and neck squamous cell carcinoma.			
Target site in the head and neck region amenable to quad-shot palliative radiotherapy, as determined by the treating radiation oncologist.			
Age 18 years or greater at time of registration			
ECOG Performance Status of 0-2.			
Women of child-bearing potential and men must agree to use adequate contraception (hormonal or barrier method of birth control; abstinence) prior to study entry and for the duration of study participation. Should a woman become pregnant or suspect she is pregnant while participating in this study, she should inform her treating physician immediately.			
Ability to understand and the willingness to sign an IRB-approved informed consent document (either directly or via a legally authorized representative).			
Willingness to provide blood and saliva samples for exploratory research purposes			

Quad-Shot Radiotherapy in Combination with Immune Checkpoint Inhibition for Advanced/Recurrent Head and Neck Cancer  
 Wake Forest Baptist Comprehensive Cancer Center  
 WFBCCC60320

Organ and Marrow Function as defined below:													
Absolute neutrophil count (ANC) $\geq 1.5 \times 10^9/L$													

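### Section 3.1.5 and the eligibility checklist accept one contraceptive method where 4.4.7.1 requires two, and the post-dose period differs across 3.1.5, 4.4.7.1 and 8.1

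*Combined protocol and SAP*

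**What the plan says.** Three sections and one form set contraception rules.

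- **Section 3.1.5 (inclusion).** Women of child-bearing potential and all men agree to "use adequate contraception (hormonal or barrier method of birth control; abstinence) prior to study entry and for the duration of study participation". The Appendix A checklist, which section 4.1 requires before registration, repeats this: patients "must agree to use adequate contraception (hormonal or barrier method of birth control; abstinence) prior to study entry".
- **Section 4.4.7.1 (restrictions during the study).** Women who could become pregnant, are sexually active and have a male partner who has not been sterilised "must use 2 methods of effective contraception from screening, and must agree to continue using such precautions for 180 days after the final dose". Men who are not sterilised and are sexually active with a partner who could become pregnant also need two methods, from Day 1 until 90 days after the final dose. The table of methods repeats in its heading that two are needed and lists barrier, intrauterine and hormonal options. The section adds: "Periodic abstinence, the rhythm method, and the withdrawal method are not acceptable methods of birth control".
- **Section 8.1, Embryo-fetal toxicity.** Women of reproductive potential are to be advised to use effective contraception during treatment and "for at least 4 months after the last dose". It gives no number or type of method and does not mention men.

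The text available contains no statement of which section governs where they differ.

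**The concern.** The checklist is what staff complete to register a patient, and it tests the 3.1.5 wording only. A patient can be recorded as meeting the contraception criterion and already be outside the restriction in 4.4.7.1. After treatment, a woman advised from 8.1 and a woman advised from 4.4.7.1 would be given different stopping points.

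Section 8.1 itself says that the drug can harm a fetus, pregnancy is an exclusion (3.2.4), and it is a reason for removal from study (6.6). Scheduled pregnancy tests after treatment end at Month 2 (6.2). Beyond that point the protocol relies on what patients have been told, and this is the period on which 4.4.7.1 and 8.1 disagree.

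**Working it through.** No planned statistic is involved. The check sets the rules side by side; the only arithmetic is on days.

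| | 3.1.5 and Appendix A | 4.4.7.1 | 8.1 |
|---|---|---|---|
| Women covered | child-bearing potential | child-bearing potential, sexually active, partner not sterilised | reproductive potential |
| Men covered | all | not sterilised, sexually active, partner could become pregnant | not addressed |
| Number of methods | one suffices | two | not stated |
| Start | before study entry | screening (women), Day 1 (men) | during treatment |
| Days after last dose, women | end of participation, undefined | 180 | at least 4 months |
| Days after last dose, men | end of participation, undefined | 90 | not addressed |

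**Number of methods.** Take a sexually active woman covered by 4.4.7.1 who uses one hormonal method. She meets 3.1.5 and the checklist. She does not meet 4.4.7.1, which asks for two methods from screening. The same holds from Day 1 for a man covered by 4.4.7.1 who relies on one barrier method.

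**Duration in women, 4.4.7.1 against 8.1.**
- Four months is 4 × 30.4 = 121.6, about 122 days. By calendar it lies between 28 + 31 + 30 + 31 = 120 days (February to May) and 31 + 31 + 30 + 31 = 123 days (July to October).
- The gap is 180 − 122 = 58 days (180 − 123 = 57 to 180 − 120 = 60).
- A woman who stops at exactly 4 months meets 8.1 and misses 4.4.7.1 by about 58 days.

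**Duration under 3.1.5.** The protocol supports three readings of when participation ends.
- *Last dose* (4.2 ends the treatment portion there): 0 days. Shortfall against 4.4.7.1 is 180 − 0 = 180 days for women and 90 − 0 = 90 for men.
- *Safety follow-up* (6.2 and 6.5, two monthly contacts): about 2 × 30 = 60 days. Shortfall is 180 − 60 = 120 days for women and 90 − 60 = 30 for men.
- *Survival follow-up* (6.5, until death): open-ended. There is no shortfall, and for a patient who outlives the 4.4.7.1 period 3.1.5 becomes the longer rule.

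**Population and start.** Section 3.1.5 covers all men and begins before study entry; 4.4.7.1 covers a subset of men and begins on Day 1. So 4.4.7.1 is not the stricter text in every respect.

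**Abstinence.** Section 4.4.7.1 applies only to sexually active patients and rejects only periodic abstinence. A completely abstinent patient satisfies both sections. The defect is that 3.1.5 uses the word without qualification, so periodic abstinence could be read as acceptable there.

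**Table reference.** Men "must use 2 acceptable methods of effective contraception (see Table 1" in the words of 4.4.7.1, but the protocol's Table 1 lists response rates to immunotherapy. The contraception table carries no number.

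**The case against.** The strongest reply is that nothing here is impossible to follow. The 4 months in 8.1 is a minimum, and 180 days satisfies it. Two methods that include a hormonal or barrier one also satisfy the method wording of 3.1.5. Section 8.1 is a general statement of drug risk, while 4.4.7 is the section headed as study restrictions. There are other safeguards: pregnancy testing at screening, as clinically indicated, and at Months 1 and 2; exclusion and removal for pregnancy; and prompt reporting of a suspected pregnancy. The scale is small: 30% of 15 patients is 0.30 × 15 = 4.5, so about 4 or 5 women, and the number who could become pregnant is not given.

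Most of this stands. It shows that the rules differ in strictness and do not exclude one another. It does not remove the inconsistency: the form used at registration tests one rule, a later section imposes another, and no text says which prevails. The rules also bind men, so the number affected is not limited to the women.

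A reader might go further and infer that patients consent to one rule and are then held to a different one. The documents do not support that. Section 4.4.7.1 applies to women from screening and itself requires their agreement to the 180 days, and the consent form was not available for review. A reader might also infer that all three sections conflict on method, number and duration. They do not: 8.1 bears only on duration, and only in women.

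**Conclusion.** The contraception rules are inconsistent in two respects.

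- **Number of methods:** one in 3.1.5 and Appendix A, two in 4.4.7.1 for the sexually active patients it covers. A patient can pass the checklist and breach 4.4.7.1.
- **Post-dose duration:** for women, 180 days in 4.4.7.1 against at least about 122 days in 8.1, a gap of about 58 days. For men, 90 days in 4.4.7.1 with 8.1 silent. The end point in 3.1.5 is undefined, so its gap against 4.4.7.1 runs from 180 days (women) or 90 days (men) to none.

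The first respect, and the 58-day gap, rest on the text alone. The size of the 3.1.5 gap rests on how participation is read. The point concerns eligibility checks, advice to patients and deviation recording; it leaves the response rate, its exact confidence interval and the 15 evaluable patients untouched. How many deviations would follow cannot be estimated from the documents.

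**What to change.** Reconcile 3.1.5, Appendix A, 4.4.7.1 and 8.1 so that the population covered, the number of methods and the post-dose duration agree, for women and for men. In the same amendment:

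- define when study participation ends for this purpose;
- state in 3.1.5 what kind of abstinence is meant;
- number the contraception table and correct the reference to it in 4.4.7.1;
- check the consent form against the reconciled text, and re-inform enrolled patients if their commitment changes.

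Which number of methods and which duration apply is for the sponsor's clinicians to decide. The cost is a wording amendment to the protocol and checklist, possibly to the consent form, with renewed information to enrolled patients if needed. Sample size and analysis do not change.

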### 3.2 Exclusion Criteria

- 3.2.1 Radiation therapy to the planned quad-shot radiotherapy target region within 30 days of registration.
- 3.2.2 Prior radiotherapy to the head and neck that precludes safe delivery of study radiotherapy, as determined by the treating radiation oncologist.
- 3.2.3 Active medical conditions that are contraindications to study radiotherapy (i.e. scleroderma), as determined by the treating radiation oncologist.
- 3.2.4 Pregnant or lactating women are excluded from this study because radiotherapy is contraindicated in pregnancy and because there is an unknown but potential risk for adverse events in nursing infants secondary to treatment of the mother with immunotherapy.
- 3.2.5 Participation in another clinical study with an investigational product during the last 3 months.
- 3.2.6 Any previous treatment with a PD1 or PD-L1 inhibitor.
- 3.2.7 Any anti-cancer therapy (chemotherapy, immunotherapy, endocrine therapy, targeted therapy, biologic therapy, tumor embolization, monoclonal antibodies, other investigational agent) within the last 30 days. Note: this excludes palliative radiotherapy to the non-target site.
- 3.2.8 Mean QT interval corrected for heart rate (QTc)  $\geq 470$  ms. except for patients with pacemaker who have a paced ventricular rhythm
- 3.2.9 Current or prior use of immunosuppressive medication within 30 days, with exceptions of intranasal and inhaled corticosteroids, a brief, non-sustained corticosteroids treatment for incidental problems such as allergies (at the discretion of the treating physician) or sustained systemic corticosteroids treatment at physiological doses, which are not to exceed 10 mg/day of prednisone, or an equivalent corticosteroid except for a short course of prednisone that is prescribed for acute allergic situations or for prevention of an allergy to contrast substance utilized for imaging studies.
- 3.2.10 Any unresolved toxicity (>CTCAE grade > 2) from previous anti-cancer therapy. Subjects with irreversible toxicity that is not reasonably expected to be exacerbated by the investigational product may be included (e.g., hearing loss, peripherally neuropathy).
- 3.2.11 Any prior Grade  $\geq 3$  immune-related adverse event (irAE) while receiving any previous immunotherapy agent, or any unresolved irAE >Grade 1.

Quad-Shot Radiotherapy in Combination with Immune Checkpoint Inhibition for  
Advanced/Recurrent Head and Neck Cancer  
Wake Forest Baptist Comprehensive Cancer Center  
WFBCCC60320

- 3.2.12 Active or prior documented autoimmune disease within the past 2 years  
NOTE: Subjects with vitiligo, Grave's disease, or psoriasis not requiring systemic treatment (within the past 2 years) are not excluded.
- 3.2.13 Active or prior documented inflammatory bowel disease (e.g., Crohn's disease, ulcerative colitis).
- 3.2.14 History of primary immunodeficiency.
- 3.2.15 History of allogeneic organ transplant.
- 3.2.16 History of hypersensitivity to any excipient in pembrolizumab.
- 3.2.17 History of pneumonitis or interstitial lung disease.
- 3.2.18 Subjects with uncontrolled seizures.
- 3.2.19 Uncontrolled intercurrent illness including, but not limited to, ongoing or active infection, symptomatic congestive heart failure, uncontrolled hypertension, unstable angina pectoris, uncontrolled cardiac arrhythmia, active peptic ulcer disease or gastritis, active bleeding diatheses, evidence of acute or chronic hepatitis B, hepatitis C or human immunodeficiency virus (HIV), or psychiatric illness/social situations that would limit compliance with study requirements or compromise the ability of the subject to give written informed consent.
- 3.2.20 Known history of active tuberculosis.
- 3.2.21 Receipt of live attenuated vaccination within 30 days prior to study entry or within 30 days of receiving pembrolizumab.
- 3.2.22 Any condition that, in the opinion of the investigator, would interfere with evaluation of study treatment or interpretation of patient safety or study results.

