### Quad-Shot Palliative Radiotherapy for Head and Neck Cancer

Palliative radiotherapy (RT) is a mainstay in the SOC treatment of recurrent or metastatic HNSCC (15). Palliative RT is primarily delivered using external-beam techniques over short courses using larger doses per fraction ( $\geq 3$  Gy per fraction) than conventionally fractionated radiotherapy (1.8-2 Gy per fraction) in an attempt to effect local tumor regression and relief of

Quad-Shot Radiotherapy in Combination with Immune Checkpoint Inhibition for  
 Advanced/Recurrent Head and Neck Cancer  
 Wake Forest Baptist Comprehensive Cancer Center  
 WFBCCC60320

malignancy-related morbidity while limiting acute toxicity. While various fractionations have been reported for this purpose, the quad-shot regimen is a commonly used SOC radiotherapy schedule derived from prior palliative experiences in advanced pelvic malignancy (16, 17). This regimen is comprised of four 3.5 to 3.7-Gy fractions delivered twice daily (BID) over the course of two consecutive days (17-22). This regimen is associated with favorable palliative response rates at the treated site (Table 2). It can also be given concurrently with cytotoxic chemotherapy as reported in two studies detailed in Table 2 (21, 23). Additionally, due to the nature of the hypofractionated regimen and its delivery in split-course cycles, acute toxicity is modest.

Table 2: Quad-Shot Palliative Radiotherapy for Head and Neck Cancer				
Study	Dose/Number of Fractions	Response Rate	Toxicity Rate	Note
Paris et al. (17)	14.8 Gy / 4	CR: 28% PR: 49%	N/A	1-3 cycles delivered with 3-4 weeks between cycles
Corry et al. (19)	14 Gy / 4	CR: 6% PR: 47%	Mucositis G1: 33%; G2: 11%; G3: 0%	1-3 cycles delivered with 3-4 weeks between cycles
Lok et al. (18)	14.8 Gy / 4	Pain response: 66%	Mucositis/dermatitis G3: 5%	1-3 cycles delivered with 3-4 weeks between cycles
Finnegan et al. (20)	14.8 Gy / 4	Pain CR: 39% Pain PR: 22%	Mucositis/dermatitis G2+: 26%/17%	1-3 cycles delivered with 3-4 weeks between cycles
Chen et al. (22)	14.8 Gy / 4	Palliative response: 83%	G3+: 9%	1-3 cycles delivered with 3-4 weeks between cycles.
Carrascosa et al.	14.8 Gy / 4	CR: 14% PR: 71%	Mucositis G3: 14%	1-3 cycles delivered with 3-4 weeks between cycles. Concurrent paclitaxel administered 1 hour prior to the first fraction of each cycle.

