### 7.1.2 Methods for Evaluation of Measurable Disease

- **Method(s) for obtaining measurements:**

All measurements should be taken and recorded in metric notation using a ruler or calipers. All baseline evaluations should be performed as closely as possible to the beginning of treatment and not more than 30 days before registration.

The same method of assessment and the same technique should be used to characterize each identified and reported lesion at baseline and during follow-up. Imaging-based evaluation is preferred to evaluation by clinical examination unless the lesion(s) being followed cannot be imaged but are assessable by clinical exam.

Clinical lesions: Clinical lesions will only be considered measurable when they are superficial (e.g., skin nodules and palpable lymph nodes) and  $\geq 10$  mm diameter as assessed using calipers (e.g., skin nodules). In the case of skin lesions, documentation by color photography, including a ruler to estimate the size of the lesion, is recommended.

- **Use of imaging techniques (e.g., x-ray, CT, MRI, PET) for measuring disease**

Imaging (CT, MRI, or PET/CT) will be obtained routinely as per clinical practice for patients being treated with immunotherapy. Either modality will be suitable for obtaining

measurements. When possible, efforts should be made to obtain the same imaging modality used for baseline imaging for all follow-up response assessments.

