Platelet count $\geq 100 \times 10^9/L$													
Hemoglobin $\geq 9.0 \text{ g/dL}$													
Serum bilirubin $\leq 1.5 \times \text{ULN}$ (institutional upper limit of normal)													
AST and ALT $\leq 2.5 \times \text{ULN}$ (institutional upper limit of normal)													
Serum creatinine CL $>40 \text{ mL/min}$ by the Cockcroft-Gault formula (Cockcroft and Gault 1976) or by 24-hour urine collection for determination of creatinine clearance:		
 
 Males:		
 
 Creatinine CL (mL/min)	= <math>\frac{\text{Weight (kg)} \times (140 - \text{Age})}{72 \times \text{serum creatinine (mg/dL)}}</math>	
 
 Females		
 
 Creatinine CL (mL/min)	= <math>\frac{\text{Weight (kg)} \times (140 - \text{Age})}{72 \times \text{serum creatinine (mg/dL)}} \times 0.85</math>	
 
	Males:		Creatinine CL (mL/min)	= $\frac{\text{Weight (kg)} \times (140 - \text{Age})}{72 \times \text{serum creatinine (mg/dL)}}$	Females		Creatinine CL (mL/min)	= $\frac{\text{Weight (kg)} \times (140 - \text{Age})}{72 \times \text{serum creatinine (mg/dL)}} \times 0.85$			
Males:													
Creatinine CL (mL/min)	= $\frac{\text{Weight (kg)} \times (140 - \text{Age})}{72 \times \text{serum creatinine (mg/dL)}}$												
Females													
Creatinine CL (mL/min)	= $\frac{\text{Weight (kg)} \times (140 - \text{Age})}{72 \times \text{serum creatinine (mg/dL)}} \times 0.85$												
													
													
													
Exclusion Criteria (as outlined in study protocol)		Criteria NOT present	Criteria is present	Source Used to Confirm * (Please document dates and lab results)									
Radiation therapy to the head and neck region within 30 days of registration.													

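### A recently irradiated lesion can serve as a target lesion without documented regrowth, so late shrinkage from off-study treatment can count in the primary response rate

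*Combined protocol and SAP*

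**What the plan says.** **Earlier treatment.** Exclusion 3.2.1 rules out "Radiation therapy to the planned quad-shot radiotherapy target region within 30 days of registration". Exclusion 3.2.7 covers other anti-cancer treatment, ending its list with "other investigational agent) within the last 30 days". It names no date from which the days are counted, and it adds: "Note: this excludes palliative radiotherapy to the non-target site". The Appendix A checklist words the radiotherapy item differently, as "Radiation therapy to the head and neck region within 30 days of registration", and its anti-cancer-therapy item has no non-target exemption.

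**Baseline imaging.** Section 7.1.2 states: "All baseline evaluations should be performed as closely as possible to the beginning of treatment and not more than 30 days before registration". Study Calendar footnote i (Section 6.1) gives the same 30-day limit for pre-study requirements. Footnote f limits the baseline CT or MRI to 14 ± 5 days before first treatment. No text ranks these rules.

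**Lesion choice and scoring.** Inclusion 3.1.1.2 admits "Locally recurrent head and neck squamous cell carcinoma not suitable for curative local treatment within or outside a previously irradiated tissue"; 3.1.1.1 and 3.1.1.3 admit locally advanced and metastatic disease. In Section 7.1.1 measurability depends on size, and the target lesions are the one or two lesions chosen for quad-shot. In Section 7.1.3 partial response is a fall of at least 30% from the baseline sum, and best overall response is taken over all time points. Section 11.1 makes the overall response rate (ORR) the primary analysis.

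**The concern.** RECIST response is a change from baseline, so it can be attributed to study treatment only if the lesion was not already shrinking from something else when the baseline was taken. Here a lesion irradiated off study shortly before registration can be measured as baseline while it is still regressing. Regression before the scan does no harm, because it is already in the baseline sum. Regression after the scan is credited to quad-shot plus pembrolizumab. The same mechanism applies to recent systemic therapy under 3.2.7.

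There is no control arm to absorb the error. Section 11.3 judges the observed rate against earlier response rates of 13% to 36%, so an upward shift bears directly on the decision about future studies.

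**Working it through.** **1. The plan's own figure.** Section 11.3 gives a maximum 95% Clopper-Pearson width of 0.52 for 15 evaluable patients, at 7/15. The exact limits at 7/15 are 0.2127 and 0.7341, a width of 0.5215. The figure reproduces.

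**2. Shortest interval from radiotherapy to baseline.** Take registration as day 0 and the last permitted day of target radiotherapy as day −31. The gap is scan day minus radiotherapy day.

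- Section 7.1.2 or footnote i alone: the scan is allowed from day −30, so −30 − (−31) = 1 day.
- Footnote f, first dose on day 0, with tolerance: the scan is allowed from −(14 + 5) = −19, so −19 − (−31) = 12 days.
- Footnote f, first dose on day 0, without tolerance: −14 − (−31) = 17 days.
- Footnote f, first dose on day 7, with tolerance: 7 − 19 = −12, so −12 − (−31) = 19 days.

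If radiotherapy on day −30 is read as permitted, each gap is one day shorter. A scan on day −30 breaches footnote f, so the 1-day gap arises only if 7.1.2 is taken to govern. A CT or MRI that satisfies every rule falls at least 12 days after radiotherapy.

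**3. Is regrowth required anywhere?**

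- The label in 3.1.1.2, locally recurrent, implies regrowth in that stratum, but no growth of the chosen lesion has to be documented. The other two strata carry no such implication.
- The measurable-lesion and target-lesion definitions in 7.1.1 contain no condition on earlier irradiation.
- Exclusion 3.2.2 concerns safe delivery. Exclusion 3.2.22 is investigator opinion and does not name recent treatment.
- Appendix A covers the target, since the target lies in the head and neck, but counts the same 30 days from registration and so does not lengthen the interval.

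**4. Effect per patient.** One added responder is 1/15 = 6.7 points. For example, 3/15 = 20.0% (95% CI 4.3 to 48.1) becomes 4/15 = 26.7% (7.8 to 55.1). A move from 5/15 = 33.3% to 6/15 = 40.0% crosses the 36% upper benchmark. A patient adds to the count only if he or she would not otherwise have responded.

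**5. Illustration with assumed inputs.** Let p₀ be the true rate, f the share of patients recently treated, and q the chance that carry-over alone produces a response in an otherwise non-responder. The observed rate is p₀ + (1 − p₀) × f × q. The documents give neither f nor q; assume f from 0.1 to 0.4 and q from 0.1 to 0.5.

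- p₀ = 0.17 (Table 1, pembrolizumab alone): from 0.17 + 0.83 × 0.01 = 0.178 to 0.17 + 0.83 × 0.20 = 0.336. That is 0.1 to 2.5 extra responders among 15. The chance of 6 or more responders rises from 3.0% to between 3.7% and 39%.
- p₀ = 0.36 (top of the benchmark range): from 0.366 to 0.488, or 0.1 to 1.9 extra responders.

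The range runs from negligible to decisive, so the effect cannot be sized from the plan.

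**6. Non-target lesions.** In the Section 7.1.3 table, every row giving overall CR or PR requires CR or PR in the target lesions. Disappearance of non-target disease can turn an overall PR into a CR, and both already count as response.

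**The case against.** The best defence is that the case is rare and partly guarded. Footnote f is the rule specific to baseline CT and MRI, and 7.1.2 itself asks for a scan close to treatment. Inclusion 3.1.2 requires that palliative radiotherapy to the site be currently recommended. Exclusion 3.2.22 lets the investigator exclude a patient whose results would be hard to interpret. The trial is an estimation pilot with no hypothesis test and an interval up to 0.52 wide. All of this limits the exposure, and footnote f, if it governs, removes the 1-day case. None of it requires regrowth, and 12 days is still a short interval.

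A reader might infer from Table 2, "1-3 cycles delivered with 3-4 weeks between cycles", that patients part-way through an off-study course would commonly enter. The documents do not support that. Study quad-shot starts no earlier than after pembrolizumab cycle 2, which is 21 days after first dose, so a patient irradiated on day −31 would wait at least 31 + 21 = 52 days.

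A reader might also take Table 2's CR plus PR rates of 6 + 47 = 53% and 28 + 49 = 77% as the size of the carry-over. They are responses after 1 to 3 cycles. They are not the chance of a further 30% fall after a later baseline, and every patient then receives study quad-shot to the same lesion, so some would have responded anyway. Nor do the documents support any particular number of affected patients.

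**Conclusion.** The point holds in a limited form. The baseline rules conflict, the shortest interval after target radiotherapy is 1 day under one rule and 12 days under the other (with dosing at registration), and neither comes with a regrowth condition. Continuing shrinkage can therefore enter the primary ORR, always upward, at 6.7 points for each otherwise non-responding patient. This rests on some patients having had recent treatment to the target and on regression continuing past the baseline scan; the documents show that both are permitted, not how often they occur.

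Two wider readings do not follow. A reader might conclude that both 30-day washouts end where the baseline window opens; that can be shown for 3.2.1 but not for 3.2.7, which has no anchor. A reader might also conclude that non-target lesions have no radiotherapy washout and so inflate the ORR. Appendix A does bar recent head and neck radiotherapy, in conflict with 3.2.1 and 3.2.7, and non-target shrinkage cannot by itself create an overall response. Its reach is the secondary non-target rate and the split between CR and PR.

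**What to change.** 1. Merge Section 7.1.2 and calendar footnotes i and f into one baseline window with one anchor date, and require the scan used for response to follow completion of the 3.2.1 and 3.2.7 washouts. The shortest interval after target radiotherapy then becomes 30 days in place of 1 or 12.
2. Anchor 3.2.7 to registration, and reconcile Appendix A with 3.2.1 and 3.2.7 on the region covered and the non-target exemption.
3. In Section 7.1.1, count a previously irradiated lesion as a target lesion for response only if it is new or has documented growth since that radiotherapy. Decide this at baseline, before any follow-up scan, so that evaluability cannot depend on outcome.
4. Record any non-target lesion irradiated shortly before registration, and do not credit its disappearance as non-target response.
5. As a check, report the ORR with and without recently treated patients.

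These are wording and measurement changes that use records and scans already collected; the target of 15 evaluable patients is unchanged. The cost is an occasional later baseline scan, or a patient who is not evaluable for response and has to be replaced.
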